8.1.3.2 Subject-level Analyses

Subject-level results will be determined for each reader based on the lesion-level result(s):

- First, each lesion will be determined as TP, TN, FP, or FN by comparing the FET PET determination to the standard of truth.
- If the subject has only one lesion, then the subject-level result (for that reader) will be the same as the lesion-level determination.
- If the subject has two or more lesions, then the subject-level result (for that reader) will be a lesion-level result according to the following hierarchy, based on the potential clinical impact of these reads.
 - TP > FP > FN > TN > Missing
 - For example, if a subject has one TP lesion and one FN lesion (according to a specific reader), then the subject-level result (according to that reader) will be TP.

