2. The goal of this study is to characterize existing lesions on the FET PET. If new lesions develop on follow-up imaging that are not in the same location or related to the original lesion of concern at time of FET PET, this will not be characterized as recurrent disease. This same issue may exist with histopathology, where a new lesion geographically distinct from the baseline lesion may be sampled and positive for tumor, but the lesion of concern was unchanged and not biopsied. The Truth Panel will take this into account when determining the characterization of the lesion.
3. Patients without imaging or histopathology due to clinical progression (hospice and/or death) will be characterized as recurrent disease.

The CSOT of progression/recurrence (positive) or TRC (negative) will be determined for each individual lesion and for each subject overall.

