8.1.3.1 Lesion-level Analyses

For lesion-specific analyses, lesions will be classified as either TP, FP, TN, or FN:

- True positive (TP): FET PET read as positive for progression/recurrence, standard of truth confirms tumor progression/recurrence.
- False positive (FP): FET PET read as positive for progression/recurrence, standard of truth does not confirm progression/recurrence.
- True negative (TN): FET PET read as negative for progression/recurrence, standard of truth confirms negative for progression/recurrence.

- False negative (FN): FET PET read as negative for progression/recurrence, standard of truth does not confirm progression/recurrence.
- For any lesion that is recorded by only one of the expected evaluations (either by a blinded reader or by the standard of truth) after receiving both evaluations, the non-recorded evaluation will be assessed as negative for determination of the lesion-specific result (TP, FP, TN, or FN).

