8.2.2 Efficacy Variables

The sensitivity and specificity of FET PET imaging will be calculated according to the above formula along with Wilson's binomial (score) 95% confidence intervals.

- **Sensitivity**

Sensitivity is defined as the proportion of study patients with a true positive (TP) FET PET scan relative to those with positive standard of truth result:

$$\text{Sensitivity (\%)} = [\text{TP} / (\text{TP} + \text{FN})] \times 100$$

- **Specificity**

Specificity is defined as the proportion of study patients with a true negative (TN) FET PET imaging result relative to those with a negative standard of truth result:

$$\text{Specificity (\%)} = [\text{TN} / (\text{TN} + \text{FP})] \times 100$$

The positive predictive value, the negative predictive value, accuracy, misclassification rate, standardized uptake value, and tumor-to-background ratio will be calculated as follows:

- **Positive predictive value (PPV)**

The positive predictive value is defined as the probability that a positive standard of truth result is obtained given that the result of the FET PET scan is positive.

$$\text{PPV (\%)} = [\text{TP} / (\text{TP} + \text{FP})] \times 100$$

- **Negative predictive value (NPV)**

The negative predictive value is defined as the probability that a negative standard of truth result is obtained given that the result of the FET PET scan is negative.

$$\text{NPV (\%)} = [\text{TN} / (\text{TN} + \text{FN})] \times 100$$

- **Accuracy**

The accuracy is defined as the probability that the FET PET scan result is correct.

$$\text{Accuracy (\%)} = [(\text{TP} + \text{TN}) / (\text{TP} + \text{FP} + \text{TN} + \text{FN})] \times 100$$

- **Misclassification Rate**

The misclassification rate is defined as the probability that the FET PET scan result is not correct.

$$\text{Misclassification Rate (\%)} = [(\text{FP} + \text{FN}) / (\text{TP} + \text{FP} + \text{TN} + \text{FN})] \times 100$$

- **Standardized Uptake Value (SUV) and Tumor-to-Background Ratio (TBR)**

Quantitative assessments will be performed on transaxial slices showing the highest FET accumulation. Quantitative analysis will be performed on the 20-40 minute imaging time point.

First, readers will determine the SUVmean of background normal tissue by marking a large region of interest (ROI) on the contralateral hemisphere in an area of unaffected brain tissue.

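### Ranking FP above FN at subject level scores some patients with recurrence as false positives, moving them from the sensitivity denominator to the specificity denominator

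*Combined protocol and SAP*

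**What the plan says.** Section 8.1.3.2 first scores every lesion against the standard of truth. For multi-lesion subjects it then applies a ranking: "If the subject has two or more lesions, then the subject-level result (for that reader) will be a lesion-level result according to the following hierarchy". The order is "TP > FP > FN > TN > Missing", and the reason given is that it is "based on the potential clinical impact of these reads". The only worked example is a subject with one TP and one FN lesion.

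Section 9.2.2 carries these labels into the co-primary endpoints. Success needs lower 95% bounds of at least 0.70 for sensitivity and 0.68 for specificity, in the same two of three (evidently readers).

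Three other places bear on the point:

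- Section 8.2.2 defines sensitivity "relative to those with positive standard of truth result" and specificity "relative to those with a negative standard of truth result". It computes them as TP/(TP+FN) and TN/(TN+FP).
- Section 8.1.2.1 says that the composite standard of truth (CSOT) "will be determined for each individual lesion and for each subject overall".
- Section 8.1.3.1 says that when only the reader or only the standard of truth has recorded a lesion, "the non-recorded evaluation will be assessed as negative for determination of the lesion-specific result".

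**The concern.** A subject's disease status should come from the standard of truth and be the same for every reader. Under the hierarchy it comes from the reader's own pattern of hits and misses. If a reader misses the recurrence and over-calls something else, the subject is counted as disease-free and misread, not as diseased and missed. A failure of sensitivity is then charged to specificity. The subject-level CSOT, which would settle the matter, is determined but not used in this step.

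The unmatched-lesion rule makes the pattern more likely. A reader mark at one site and a truth lesion at another give one FP plus one FN, so a recurrence that the reader wrongly located is scored FP. At stake are both co-primary estimates, in a study meant to support a New Drug Application (Section 1.1).

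**Working it through.** **1. Which steps of the order are at fault.** FN is taken in its evident sense (read negative, truth positive), which the Section 8.2.2 formula requires; the FN line in Section 8.1.3.1 is worded otherwise. A subject with at least one truth-positive lesion is taken to be truth-positive.

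| Lesion results, one reader | Subject truth | Label | Denominator used |
|---|---|---|---|
| TP with any of FP, FN, TN | positive | TP | sensitivity, correct |
| FN and TN | positive | FN | sensitivity, correct |
| FP and TN | negative | FP | specificity, correct |
| FN and FP, no TP | positive | FP | specificity, **wrong** |

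Only FP > FN moves a subject across truth classes.

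**2. Reader dependence.** Let lesion A be recurrent and lesion B treatment change. Reader 1 calls A: TP. Reader 2 calls only B: FP. Reader 3 calls neither: FN. The same patient is in the sensitivity denominator for readers 1 and 3 and in the specificity denominator for reader 2.

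**3. The plan's sample size.** Section 9.1.1 gives N=118 at prevalence 0.50, sensitivity 0.81 and specificity 0.79. This does not reproduce. With the two-sided 95% Wilson bound and exact binomial power of at least 0.80, 120 truth-positive and 126 truth-negative subjects are needed. That is a separate matter; N=118 serves here only to set the illustration at 118 × 0.50 = 59 per class.

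**4. Illustration.** The Wilson lower bound is [p + z²/2n − z√(p(1−p)/n + z²/4n²)] / (1 + z²/n), with z = 1.96. For 48/59: (0.8461 − 0.1046)/1.0651 = 0.696. Let k missed-recurrence subjects also have an over-called lesion. The hierarchy then gives sensitivity 48/(59−k) and specificity 48/(59+k).

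| k | Sensitivity (bound vs 0.70) | Specificity (bound vs 0.68) | Reader |
|---|---|---|---|
| 0 | 48/59 (0.696, fails) | 48/59 (0.696, passes) | fails |
| 1 | 48/58 (0.711, passes) | 48/60 (0.682, passes) | passes |
| 2 | 48/57 (0.726, passes) | 48/61 (0.669, fails) | fails |

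The opposite flip also exists. With 49/59 (0.715) and 48/59 (0.696) a reader passes both; with k = 2, specificity 48/61 (0.669) fails.

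**5. Average effect.** Let q be the share of missed-recurrence subjects who also have an over-called lesion. The documents give no value, so q is an assumption. With equal classes, reported sensitivity is Se/[Se + (1−Se)(1−q)] and reported specificity is Sp/[1 + (1−Se)q]. At q = 10%: 0.81/0.981 = 0.826 and 0.79/1.019 = 0.775. The last two columns are exact binomial results for one reader, shown as 59 / 118 per class. The last treats the endpoints as independent.

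| q | Reported sens./spec. at true 0.81/0.79 | Chance of passing the sensitivity bound at true sensitivity 0.70 | Chance of passing both at true 0.81/0.79 |
|---|---|---|---|
| 0 | 0.810 / 0.790 | 1.7% / 2.1% | 0.168 / 0.565 |
| 5% | 0.818 / 0.783 | 2.9% / 4.0% | 0.189 / 0.586 |
| 10% | 0.826 / 0.775 | 4.7% / 6.6% | 0.198 / 0.559 |
| 20% | 0.842 / 0.761 | 9.7% / 16.6% | 0.186 / 0.465 |
| 30% | 0.859 / 0.747 | 18.1% / 34.6% | 0.154 / 0.354 |

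**The case against.** The order is deliberate. It ranks by clinical impact and puts scan-positive results (TP, FP) above scan-negative ones (FN, TN). Calling the mixed subject FP keeps a patient with a positive scan out of NPV, which Section 8.2.2 conditions on a negative scan. This stands in part: relabelling the subject FN creates the opposite difficulty for NPV, and the fix has to deal with it. It does not justify the present rule for sensitivity and specificity, whose denominators depend on truth and not on the read.

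The pattern may also be rare. Single-lesion subjects are untouched unless an unmatched mark adds a lesion, and the prespecified lesion-level analyses still show each miss and over-call. That limits the size but does not repair the co-primary endpoints. Accuracy and misclassification rate would not reveal the shift, because FP+FN is unchanged.

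Three stronger readings are tempting and are not supported:

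- A reader might infer that the rule makes the study easier to pass. The two biases oppose each other under a both-must-pass criterion. With specificity at 47/59 (bound 0.677), for example, a reader fails before any shift, and one shift lowers the bound to 0.664 (47/60).
- A reader might infer that every subject with an FN and an FP lesion is misplaced. One who also has a TP lesion is labelled TP, which is the right class.
- A reader might infer that the majority-rule summary has no fixed truth. Section 8.2.1 takes the majority over positive or negative reads, which can be compared with one fixed CSOT. The success criterion does not mention that summary.

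**Conclusion.** The point holds for the FP > FN step only, and as a matter of logic. For a given reader, any subject with at least one FN lesion, at least one FP lesion and no TP lesion is counted in the wrong truth class, and nothing elsewhere in the plan restores the subject. Sensitivity is biased up and its own bound becomes anti-conservative; specificity is biased down. One subject can change a reader's result near the thresholds, in either direction. How often this would happen cannot be derived from the documents: 59 per class and every q above zero are assumptions. The conclusion does not depend on N=118.

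**What to change.** Set the truth class from the subject-level standard of truth, identically for all readers:

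- Truth-positive subject: TP if at least one truth-positive lesion is read positive, otherwise FN.
- Truth-negative subject: FP if any lesion is read positive, otherwise TN.
- Subject called recurrent on clinical decline with no lesion-level truth (Section 8.1.2.1): TP if any lesion is read positive, otherwise FN. Without this line, a positive scan in such a patient could be scored FN.

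Apply the same truth-class rule to the histopathology standard, and compare the majority-rule read with the same fixed truth. Report over-called lesions in truth-positive subjects at lesion level.

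For subject-level PPV and NPV, state that FN means no recurrent lesion was detected. Report how many FN subjects had a positive read elsewhere, and give NPV with and without them. In the k = 1 illustration that is 48/59 = 0.814 with the subject and 48/58 = 0.828 without.

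The cost is a few lines of text and programming, with no new data. Sensitivity may be slightly lower than under the present rule, and NPV needs the extra note. The change should be made before the reads are scored against truth.

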8.2 Efficacy Analysis Variables

8.2.1 General Efficacy Analyses

Sensitivity, specificity, positive predictive value, negative predictive value, accuracy, and misclassification rate will be presented per subject by individual reader. There will also be a majority rule summary of the three readers' results where the calculations are based on the FET PET result (positive or negative) agreed to by the majority of the readers (2 or 3 readers). Wilson's binomial (score) 95% confidence intervals will be presented for each reader and for majority rule result.

Standardized uptake value (SUV) and tumor-to-background ratio (TBR) will be summarized per lesion for each reader. Individual readers' results will be presented in a listing.

8.2.2 Efficacy Variables

The sensitivity and specificity of FET PET imaging will be calculated according to the above formula along with Wilson's binomial (score) 95% confidence intervals.

- **Sensitivity**

Sensitivity is defined as the proportion of study patients with a true positive (TP) FET PET scan relative to those with positive standard of truth result:

$$\text{Sensitivity (\%)} = [\text{TP} / (\text{TP} + \text{FN})] \times 100$$

- **Specificity**

Specificity is defined as the proportion of study patients with a true negative (TN) FET PET imaging result relative to those with a negative standard of truth result:

$$\text{Specificity (\%)} = [\text{TN} / (\text{TN} + \text{FP})] \times 100$$

The positive predictive value, the negative predictive value, accuracy, misclassification rate, standardized uptake value, and tumor-to-background ratio will be calculated as follows:

- **Positive predictive value (PPV)**

The positive predictive value is defined as the probability that a positive standard of truth result is obtained given that the result of the FET PET scan is positive.

$$\text{PPV (\%)} = [\text{TP} / (\text{TP} + \text{FP})] \times 100$$

- **Negative predictive value (NPV)**

The negative predictive value is defined as the probability that a negative standard of truth result is obtained given that the result of the FET PET scan is negative.

$$\text{NPV (\%)} = [\text{TN} / (\text{TN} + \text{FN})] \times 100$$

- **Accuracy**

The accuracy is defined as the probability that the FET PET scan result is correct.

$$\text{Accuracy (\%)} = [(\text{TP} + \text{TN}) / (\text{TP} + \text{FP} + \text{TN} + \text{FN})] \times 100$$

- **Misclassification Rate**

The misclassification rate is defined as the probability that the FET PET scan result is not correct.

$$\text{Misclassification Rate (\%)} = [(\text{FP} + \text{FN}) / (\text{TP} + \text{FP} + \text{TN} + \text{FN})] \times 100$$

- **Standardized Uptake Value (SUV) and Tumor-to-Background Ratio (TBR)**

Quantitative assessments will be performed on transaxial slices showing the highest FET accumulation. Quantitative analysis will be performed on the 20-40 minute imaging time point.

First, readers will determine the SUVmean of background normal tissue by marking a large region of interest (ROI) on the contralateral hemisphere in an area of unaffected brain tissue.

Second, a volume of interest will be placed around the lesion, and within that volume a threshold segmentation will be performed using a lower limit threshold of background SUVmean x 1.6.

Third, a 1.6 cm diameter circular ROI will be centered on the qualitatively hottest portion of FET uptake. TBRmax will be calculated by dividing the SUVmean of the 1.6 cm diameter circular ROI by the SUVmean of background normal tissue. TBRmean will be calculated by dividing the SUVmean of the lesion volume of interest (using the background SUVmean x 1.6 threshold) by the SUVmean of background normal tissue. Lesions will be quantitatively evaluated in a binary fashion as recurrence if TBRmax >

2.3 or treatment-related changes if TBRmax < 2.3. For indeterminate lesions, readers can use TBRmean to evaluate for recurrence vs. treatment-related changes.

Additionally, the SUVmax of the lesion and the SUVpeak will also be calculated.

9 Statistical Considerations and Evaluation of Results

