5.2.1 Other Modalities or Procedures

5.2.1.1 PET Imaging

Participants may undergo sedation as required in order to successfully undergo imaging. Sedation or anesthesia will be administered per institutional protocol.

Study participants will undergo the FET PET imaging after all screening and baseline assessments have been completed. The radiopharmaceutical will be administered while the

patient is in the PET scanner, and imaging will last for 40 minutes. Acquired PET data will be reconstructed so that three time points are created:

1. Perfusion: 60-second acquisition that starts immediately when activity is noted in the field of view.
2. Equilibrium: 10-minute acquisition acquired between 10 and 20 minutes after injection.
3. Washout: 10-minute acquisition acquired between 30 and 40 minutes after injection.

Additionally, a 20 minute acquisition will be reconstructed between 20 and 40 minutes after injection to match the analysis performed in Lohmann et al (8).

Each study will be reviewed by a board-certified nuclear medicine physician and neuroradiologist within seven working days of the completion of the study, and a formal report will be dictated. This will be performed separately from the final analysis. The imaging findings on FET PET will be provided to the neurosurgeon and can be used in addition to MRI for planning of biopsy and surgery. For patients who received subsequent surgery, if possible the multi-parametric imaging examination will be used to target 1-4 tissue samples that have distinct metabolic findings for distinguishing recurrent disease from treatment effects.

If imaging is performed on a PET/MRI, a gadolinium-based contrast will be administered. The patient's eGFR will be checked and gadolinium will be administered per radiology department guidelines. The MRI protocol will include the clinical standard MRI. The MRI protocol may also contain research sequences such as novel sequences used for attenuation correction on PET/MRI (ie ZTE or zero echo time) and MRI spectroscopy sequences.

Optional repeat FET PET imaging will be offered to adult patients.

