9.2.3 Analysis of Secondary Endpoints

For the secondary endpoints for performance characteristics, both the composite reference standard and histopathology alone will be used in separate calculations. Only the efficacy analysis set will be analyzed for secondary efficacy endpoints; the per protocol population will not be analyzed. TP, FP, FN, and TN are defined as described in [Section 8.1.3](#).

Calculations will be done to determine the subject-specific and lesion-specific sensitivity, specificity, positive predictive value, negative predictive value, accuracy, and misclassification rate for FET PET. These analyses will use the blinded readers' overall assessment, not the visual/qualitative or quantitative assessments.

For the secondary analyses of sensitivity, specificity, PPV, NPV, accuracy, and misclassification rate that use histopathology as the standard of truth, analysis will be performed only on subjects who have known histopathology status. No imputation will be made for these endpoints.

Inter-reader variability will be analyzed using Fleiss' kappa statistic to determine the agreement between three independent blinded readers in assessing FET PET images as recurrence or TRC. Separate analyses of inter-reader variability will be done for the readers' qualitative/visual assessments, quantitative assessments, and overall assessments.

Intra-reader variability will be analyzed based on a random sample of 15 subjects whose images were re-reviewed by the same reader. The percent of agreement between the two interpretations will be computed for each reader. Cohen's kappa statistics will be used to determine the reproducibility of the assessment by individual readers when analyzing the same data repeatedly. Separate analyses of intra-reader variability will be done for the reader's qualitative/visual assessments, quantitative assessments, and overall assessments.

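### The plan gives no interval method for lesion-level accuracy that allows for several lesions in one patient; Wilson, the only interval it names, would be too narrow on pooled lesions

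*Combined protocol and SAP*

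**What the plan says.** Section 2.2 lists six accuracy measures at lesion level under secondary objective 1 (histopathology) and the same six under secondary objective 2 (composite standard of truth), which makes twelve lesion-level endpoints. Section 9.2.3 repeats the plan to compute "subject-specific and lesion-specific sensitivity, specificity, positive predictive value, negative predictive value, accuracy, and misclassification rate for FET PET" and names no interval. Section 8.1.3.2 has a hierarchy for subjects with two or more lesions, so multi-lesion patients are foreseen.

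Wilson's interval is the only one in the plan. In Section 8.2.1 the six measures, down to "accuracy, and misclassification rate will be presented per subject by individual reader", are followed in the same paragraph by the statement that "Wilson's binomial (score) 95% confidence intervals will be presented for each reader and for majority rule result". Section 8.2.2, the only place with the formulas, opens by saying that sensitivity and specificity "will be calculated according to the above formula along with Wilson's binomial (score) 95% confidence intervals", and then continues: "Sensitivity is defined as the proportion of study patients with a true positive (TP) FET PET scan". Specificity is defined in the same per-patient way.

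Clustering, a robust variance and any other allowance for correlated lesions are not mentioned anywhere.

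**The concern.** An analyst who follows the plan to the lesion-level endpoints finds one set of formulas and one interval. The natural step is to pool all lesions and apply Wilson. That interval assumes independent binary results.

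Lesions in one patient are unlikely to be independent. They come from one scan and one treatment history. Under Section 8.2.2 the background uptake value is the denominator of both tumor-to-background ratios and sets the segmentation threshold, so an error in it moves every lesion that uses it in the same direction. Section 8.1.2.1 has each lesion's truth call considered together with the patient-level determination. Under Section 8.1.3.1 a lesion that only the reader records is scored negative on truth, so several extra positive marks in one patient become false positives together.

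At stake is the stated precision of lesion-level results under two of the five secondary objectives, in a study meant to support a New Drug Application. If the method is left open, it will be chosen after the data are seen.

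**Working it through.** The plan states no figure for a lesion-level interval, so there is none to reproduce. The check asks how far pooled Wilson would be off.

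**Inputs from Section 9.1.1:** N = 118, prevalence 0.50 and sensitivity 0.81. These give 118 × 0.50 = 59 truth-positive patients. The 118 serves here only to set a realistic scale; whether it is right for the primary endpoints is a separate question.

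**Assumptions (not in the documents):** truth-positive lesions per truth-positive patient, and ICC ρ of 0.2, 0.5 or 0.8.

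**Formulas.** With m_i lesions in patient i and n = Σm_i:

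- q = Σm_i² / Σm_i
- design effect D = 1 + (q − 1)ρ
- approximate coverage of a nominal 95% interval = 2Φ(1.96/√D) − 1
- Wilson limits = [p + z²/(2n) ± z√(p(1−p)/n + z²/(4n²))] / (1 + z²/n); the cluster-adjusted version replaces n by n/D

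Example, all patients with two lesions, ρ = 0.5: D = 1 + (2 − 1) × 0.5 = 1.5; 1.96/√1.5 = 1.600; coverage 2Φ(1.600) − 1 = 0.890.

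Example, 20% with two lesions: 47 patients with one and 12 with two give n = 71 and q = (47 + 48)/71 = 1.338. At ρ = 0.5, D = 1.169, and coverage is 0.930.

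The simulation drew each patient's detection probability from a beta distribution with mean 0.81 and intra-patient correlation ρ, pooled the lesions and applied Wilson (40,000 runs).

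| Truth-positive lesions per patient | n | Formula, ρ = 0.2 / 0.5 / 0.8 | Simulated, ρ = 0.2 / 0.5 / 0.8 |
|---|---|---|---|
| One each | 59 | 0.950 / 0.950 / 0.950 | 0.955 / 0.957 / 0.954 |
| 20% have two | 71 | 0.942 / 0.930 / 0.918 | 0.922 / 0.909 / 0.896 |
| All have two | 118 | 0.926 / 0.890 / 0.856 | 0.915 / 0.877 / 0.836 |
| All have three | 177 | 0.902 / 0.834 / 0.776 | 0.896 / 0.826 / 0.763 |

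**Width, two lesions each (n = 118), observed sensitivity 0.81.** Pooled Wilson: centre (0.81 + 0.0163)/1.0326 = 0.800, half-width 1.96 × 0.0371/1.0326 = 0.070, so 0.730 to 0.871. Adjusted limits:

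- ρ = 0.2 (n/D = 98.3): 0.721 to 0.875, 1.09 times as wide
- ρ = 0.5 (n/D = 78.7): 0.710 to 0.881, 1.22 times as wide
- ρ = 0.8 (n/D = 65.6): 0.699 to 0.887, 1.33 times as wide

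**The case against.** A reader might infer that the plan assigns Wilson intervals to the lesion-level results and so chooses a wrong method. The documents do not support that. The Wilson sentence in Section 8.2.1 belongs to a per-subject paragraph, Section 8.2.2 defines its proportions over patients, and Section 9.2.3 names no interval. The sentence in Section 8.2.2 also covers sensitivity and specificity only; the other four measures get Wilson only through the per-subject paragraph. This objection stands, so the defect is a missing method, with Wilson as the likely default.

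Three other tempting arguments fail. Section 5.2.1.1 says that imaging "will be used to target 1-4 tissue samples that have distinct metabolic findings", but these are tissue samples, several may come from one lesion, and they say nothing about lesions per patient. A common reader or Truth Panel does not in itself create clustering by patient, because results are computed reader by reader and the plan describes one panel for all patients. That patients with many lesions carry more weight is true of any pooled proportion, but it concerns the point estimate and not the interval.

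The size is also open to challenge. The efficacy dataset is limited to glioma, and the documents do not say how many lesions such patients have. Sensitivity uses only truth-positive lesions and specificity only truth-negative ones, so the relevant counts can be below the total per patient. Simulated coverage at exactly 0.81 is also partly low because the binomial is discrete. Across true sensitivities of 0.79 to 0.82, coverage with 20% of patients having two lesions runs from about 92% to 95% at ICC 0.2 and about 91% to 94% at ICC 0.5. With 10% having two lesions it is about 94-95% and 93-95%. These points limit the size; they do not supply the missing method.

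Finally, lesion-level results carry no threshold or success rule, and both objectives also have subject-level results. That is correct and limits the consequence.

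**Conclusion.** The point holds as a gap. Twelve secondary endpoints are at lesion level, multi-lesion patients are expected, no interval is named for these endpoints, and the one interval in the plan would be too narrow if lesions were pooled and positively correlated.

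The size depends on two quantities that the documents do not give. It is nil if nearly every patient has one lesion, small if a minority have two, and material if two or three lesions are typical and ICC is about 0.5: coverage of about 88% and 83% in place of 95%. These figures assume 59 truth-positive patients, sensitivity 0.81 and a beta-binomial model.

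A reader might go on to doubt the study's main result. That does not follow: Section 9.2.2 sets the success rule on subject-level results, where each patient counts once per reader. This is a cheap improvement to the secondary analyses.

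**What to change.** In Sections 8.2.2 and 9.2.3, state that Wilson intervals apply to subject-level results only. For lesion-level results, name a 95% interval with the patient as cluster, for example one of these:

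- Wilson on the effective sample size n/D, with D estimated as the ratio-estimator (Rao-Scott) variance of the pooled proportion divided by p(1−p)/n.
- GEE with a robust variance, plus a small-sample correction when few patients have more than one lesion.

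A patient-level bootstrap is not a good choice with few clusters, where it is least reliable. The same rule should cover all six measures under both standards of truth, for each reader and for any majority-rule summary at lesion level. Report the number of lesions per patient, overall and in each denominator, so that the effect of clustering can be judged.

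Neither method changes the point estimate, so patients with many lesions keep their weight in it.

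The cost is a sentence or two, a few lines of code and somewhat wider lesion-level intervals. No new data or patients are needed, and the primary analysis stays as it is.
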